#### Visual analogue Pain and Pruritus visual analogue scores:

Pain visual analogue scale Instructions: "Please think about any **leg pain** you may have had over the past **2 weeks** and draw a vertical line along the scale that best describes it best."

Pruritus visual analogue scale Instructions: "Please think about any **leg itching** you may have had over the past **2 weeks** and draw a vertical line along the scale that best describes it best."

## Quality of life: EQ-5D-5L

Under each heading, please tick the ONE box that best describes your health TODAY

#### MOBILITY I have no problems in walking about I have slight problems in walking about I have moderate problems in walking about I have severe problems in walking about I am unable to walk about **SELF-CARE** I have no problems washing or dressing myself I have slight problems washing or dressing myself I have moderate problems washing or dressing myself I have severe problems washing or dressing myself I am unable to wash or dress myself **USUAL ACTIVITIES** (e.g. work ,study, housework, family or leisure activities) I have no problems doing my usual activities I have slight problems doing my usual activities I have moderate problems doing my usual activities I have severe problems doing my usual activities I am unable to do my usual activities **PAIN / DISCOMFORT** I have no pain or discomfort I have slight pain or discomfort I have moderate pain or discomfort I have severe pain or discomfort I have extreme pain or discomfort **ANXIETY / DEPRESSION** I am not anxious or depressed I am slightly anxious or depressed I am moderate anxious or depressed I am severely anxious or depressed I am extremely anxious or depressed

©EuroQoL Group 1990

Confidential – This document and the information contained herein ma without written permission from North Cumbria Integrated Care NHS Fc  $\,$ 

 
We would like to know how good or bad your health is TODAY.
 
This scale is numbered from 0 to 100.
 
100 means the best health you can imagine.
 
0 means the worst health you can imagine
 
Mark an X on the scale to indicate how your health is TODAY.
 
Now, please write the number you marked on the scale in the box below
 
YOUR HEALTH TODAY =
 
YOUR HEALTH TODAY =
 
				The best healt	

 
This scale is numbered from 0 to 100.
 
100 means the best health you can imagine.
 
0 means the worst health you can imagine
 
Mark an X on the scale to indicate how your health is TODAY.
 
Now, please write the number you marked on the scale in the box below
 
YOUR HEALTH TODAY =
 
90
 
45
 
90
 
46
 
47
 
48
 
40
 
45
 
40
 
46
 
46
 
47
 
48
 
49
 
49
 
40
 
40
 
41
 
42
 
44
 
45
 
46
 
46
 
46
 
47
 
48
 
49
 
49
 
40
 
40
 
40
 
41
 
42
 
44
 
44
 
45
 
46
 
46
 
46
 
47
 
48
 
49
 
49
 
49
 
40
 
40
 
40
 
41
 
42
 
44
 
44
 
45
 
46
 
46
 
47
 
48
 
49
 
49
 
49
 
40
 
40
 
41
 
42
 
44
 
44
 
45
 
46
 
46

	•	We would like to know how go	od or bad your health is TODAY.	you can imagi	

 
100 means the best health you can imagine.
 
0 means the worst health you can imagine
 
Mark an X on the scale to indicate how your health is TODAY.
 
Now, please write the number you marked on the scale in the box below
 
YOUR HEALTH TODAY =
 
	•	This scale is numbered from (	) to 100 .	Ŧ	

 
0 means the worst health you can imagine
 
Mark an X on the scale to indicate how your health is TODAY.
 
Now, please write the number you marked on the scale in the box below
 
80
 
75
 
70
 
65
 
60
 
55
 
60
 
45
 
40
 
35
 
30
 
25
 
20
 
15
 
	•	100 means the best health yo	u can imagine.	Ŧ	95

 
Mark an X on the scale to indicate how your health is TODAY.
 
Now, please write the number you marked on the scale in the box below
 
YOUR HEALTH TODAY =
 
90
 
90<

		0 means the worst health yo	u can imagine	Ŧ	90

 
Now, please write the number you marked on the scale in the box below
 
Your HEALTH TODAY =
 
50
 
45
 
40
 
35
 
30
 
25
 
20
 
15
 
	•	Mark an X on the scale to indic	cate how your health is TODAY.	Ŧ	85
YOUR HEALTH TODAY =	•	Now, please write the number	you marked on the scale in the box below	-	80
YOUR HEALTH TODAY = 66 40 45 40 45 40 45 40 45 40 45 40 45 40 45 40 45 40 45 40 45 40 45 40 45 40 45 40 45 40 45 40 45 40 45 40 45 40 45 45 40 45 45 45 45 45 45 45 45 45 45				手	75
YOUR HEALTH TODAY = 60 45 40 45 40 45 40 45 40 45 40 45 40 45 40 45 40 45 40 45 40 45 40 45 40 45 40 45 40 45 40 45 45 40 45 45 45 45 45 45 45 45 45 45				-	70
YOUR HEALTH TODAY = 55 60 45 40 35 30 25 20 15				圭	65
10000000000000000000000000000000000000				1	60
10000000000000000000000000000000000000				重	55
		TOOR REALTH TODAT -		1	
				Ŧ	
35 30 25 20 15				Ŧ	45
30 25 20 15				Ŧ	40
				圭	35
20 15				-	30
15				-	25
				1	20
				圭	15
				1	10

The worst health you can imagine 5

0

©EuroQoL Group 1990

#### APPENDIX 2. INTERVENTION DEVIATION AND LEG ULCER INFECTION

There may be incidences where a participant may either:

- Develop a reaction to the allocated dressing/bandage
- Becomes completely non-compliant (possibly due to bandaging being uncomfortable, or eg hospital admission)
- Improve to such an extent that compression bandaging is no longer indicated.

In such instances the patient and/or clinician can opt to stop or pause treatment with the bandage in question. If this occurs, this needs to be recorded (date and reason), and the decision can then be made to either:

- Discontinuation due to improvement in symptoms (including wound healed). Participant will still continue to be assessed as per planned dates and timepoints.
- Change over to an alternative compression bandage that is not the originally allocated type. This is allowed but only if there are clinical indications to do so or at patient request if they cannot tolerate the allocated bandage type. Patient can later in trial period be transferred back to original allocated bandage type if required.
- Pausing or discontinuation of compression bandaging when not clinically indicated. Even if leg ulcer persists and patient no longer wears compression bandage, they can still continue in the trial if they wish. Outcome measures will continue to be recorded as per planned dates and timepoints.
- Pause of compression therapy due to adverse event. Patient can remain in trial provided they are capable to continue with follow-up schedule and completion of outcome measures. If not possible, see next point regarding 'Withdraw patient from study'.
- Withdraw patient from study.
  - At the request of the patient
  - For clinical reasons, eg if the leg has deteriorated to such an extent that emergency surgical or medical intervention is required which means return to use of compression bandage in reasonable time frame is not feasible. In this case, this needs to be reported as a (Serious) Adverse Event if discontinuation is due to deterioration of the index wound or index leg only.

When overall trial participation for a patient is finished early, the participant will still be asked to complete the relevant questionnaires (provided they have capacity to do so):

- Week 6 VEINES QoL questionnaire (if patient withdrawal before week 6)
- Week 12 VEINES QoL questionnaire (if patient withdrawal > week 6 and < week 12)

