## 3. INVESTIGATIONAL DEVICES

Two different two-layer compression bandages will be appraised. Apart from Andoflex TLC Calamine Lite, provided free of charge by Milliken Healthcare Inc as part of the non-restricted research grant for this study, the other bandage (Coban 2 Lite) will be purchased by the relevant healthcare provider via the conventional Trust NHS supply chain. Coban 2 is a first-line product listed in North Cumbria Integrated Care NHS Trust's current formulary (Appendix 3). Therefore, Coban2 Lite effectively is the treatment as usual arm.

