#### 6. SUBJECTS

#### 6.1 Anticipated number of research subjects

Locally, we have healing data available from two previous trials involving venous leg ulcers, namely the PREVUE and APRICOT trials (Jonker et al 2020a, and Jonker et al 2020b). One caveat is that those

studies concerned pure venous leg ulcers and that compression bandaging could be full (40 to 50mmHg) or Lite (20 to 30 mmHg). Nonetheless, from these studies we know that the study followup time points are valid and APRICOT compared Andoflex vs Coban2.

Below a summary is given for the sample size needed. The primary outcome, wound status (healed vs non-healed) is used for sample size calculation. The non-inferiority related sample size calculation has been performed using the calculator at https://www.sealedenvelope.com/power/binary-noninferior/. Power calculations for sample size assume 80% power and 2.5% one-sided confidence interval. The non-inferiority limit is set at 15% in favour of the Coban2 control bandage. The result is shown in Table 4. Since some patients may withdraw over the course of the 12-week trial period, a 10% dropout rate is calculated into the sample size. A 1:1 allocation to the two types of compression bandage will be applied.

	Sample size calculation	
	Intervention Bandage (Andoflex)	Control Bandage (Coban2)
Ulcer healed	65%	50%
Ulcer not healed	35%	50%
	Sample size required without any du Sample size with 10% attrition rate Total of 92 patients: - 46 Patients to receive Ando - 46 Patients to receive Coba	flex

Table 4, Sample size calculations

The CONSORT guidelines require a statement on the number of patients assessed for eligibility (Schulz, Altman & Moher 2010). The number of patients screened but who did not meet the inclusion criteria or who declined to participate will be recorded, as will any patients who are lot to follow-up (Appendix 5).

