## 8.2 Primary outcome statistics

The primary objective for this pilot study wound healed status at week 12. For non-inferiority analysis, patients who withdraw prior to completion of the study or do not attend week 12 appointment will be assigned the worst-case healing outcome (not healed at week 12).

The test for non-inferiority concerns the proportion of patients attaining ulcer closure by week 12 for both treatment groups, and the associated 97.5% one-sided confidence interval for the difference. Non-inferiority of Andoflex is considered valid if the lower limit of the 95% confidence interval for the difference between treatment means (Andoflex – Coban2) is not more negative than -15%. That is, non-inferiority for Andoflex is demonstrated when a maximum of 15% fewer patients using this bandage, compared with patients using Coban2, have healed by week 12 of treatment. This approach was taken in previous non-inferiority trials for ulcers (Harding et al, 2012; Moffatt et al, 2019), and is outlined in papers by Oczkowski (2014) and Flight (2016).

For comparative performance (superiority) analysis, any statistically significant difference (p-value < 0.05) between the two treatment arms will be determined with Chi-squared test. This will be done since Dunn et al postulate that non-inferiority and superiority trials effectively aim to answer the same hypothesis (Dunn et al, 2018)

Analysis will be performed on a per protocol and also an intention to treat basis. Multiple imputation (default five imputations) will be applied for missing values for the outcome measures, and inferential statistics will be performed on pooled data. Data will first be collated in Microsoft Excel, followed by analyses performed using SPSS v20.

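### Section 8.2 does not say whether the intention-to-treat or the per-protocol analysis decides non-inferiority, and permitted bandage changes can bias either one towards the claim

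*Protocol*

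**What the plan says.** **Decision rule.** Section 8.2 calls Andoflex non-inferior if the lower limit of the 95% confidence interval for the difference in healed proportions at week 12 (Andoflex minus Coban2) is not below -15 points. Section 6.1 sets the same margin: "The non-inferiority limit is set at 15% in favour of the Coban2 control bandage". Section 8.2 then adds: "Analysis will be performed on a per protocol and also an intention to treat basis". It does not rank the two analyses, does not require both to pass, and does not say how a patient who changed bandage is classed.

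**Bandage changes.** Appendix 2 lists what may happen when the allocated bandage is stopped or paused. One option is: "Change over to an alternative compression bandage that is not the originally allocated type". It is limited to clinical indication, or to the patient's request when the allocated bandage is not tolerated. The date and reason must be recorded. A return is possible: "Patient can later in trial period be transferred back to original allocated bandage type if required".

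**Likely replacement.** Appendix 2 neither names nor excludes the other trial bandage. Section 3 says: "Therefore, Coban2 Lite effectively is the treatment as usual arm". Appendix 3 lists Coban 2 and Coban 2 Lite as the only multi-layer compression bandages. It also lists a short-stretch bandage, hosiery and leg wraps.

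**The concern.** In a superiority trial, patients who take up the other arm's treatment usually make a positive result harder to reach. In a non-inferiority trial, if the new treatment is worse, they make it easier. Under intention-to-treat, an ulcer that heals after a change from Andoflex to Coban2 Lite counts as an Andoflex success, and the arms look more alike than the bandages are.

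A per-protocol analysis is the usual companion, but it can be biased in the same direction. Patients doing badly are the ones likely to change, so removing them can leave an Andoflex group with too good a prognosis.

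Since either analysis can mislead, it matters which one carries the claim. As 8.2 stands, two results would be read against one limit, and nothing prevents the favourable one from being chosen after the data are seen. What is at stake is the stated one-sided 2.5% error rate.

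**Working it through.** **Inputs from the protocol.** Section 6.1: "Power calculations for sample size assume 80% power and 2.5% one-sided confidence interval"; margin 15 points; planned healing 65% on Andoflex and 50% on Coban2 (Table 4); "A 1:1 allocation to the two types of compression bandage will be applied"; 46 per arm. Section 8.2 counts withdrawals and missed week-12 visits as not healed, so all 46 stay in the intention-to-treat denominator.

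**Assumed, not in the protocol.** The share *s* of the Andoflex arm that changes to Coban2 Lite, and that changers heal at the full 12-week Coban2 rate.

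**1. The plan's sample size.** n per arm = (1.960 + 0.842)² × (0.65×0.35 + 0.50×0.50) / (0.15 + 0.15)² = 7.85 × 0.4775 / 0.09 = 41.6, so 42 per arm and 84 in total. With 10% added, 84 × 1.1 = 92.4, which agrees with the stated 92.

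**2. False claim under intention-to-treat.** Put Andoflex exactly on the margin: Coban2 0.50, Andoflex alone 0.35. The Andoflex arm then heals at

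p_A = 0.35(1 - s) + 0.50s.

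The trial passes if d - 1.96 × √[p̂_A(1 - p̂_A)/46 + p̂_C(1 - p̂_C)/46] is not below -0.15, where d is the observed difference. Summing the two binomial distributions exactly gives:

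| s | p_A | Expected difference | Chance of passing |
|---|---|---|---|
| 0% | 0.350 | -15.0 points | 2.4% |
| 10% | 0.365 | -13.5 points | 3.3% |
| 20% | 0.380 | -12.0 points | 4.6% |
| 40% | 0.410 | -9.0 points | 8.2% |

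Check at s = 20% by normal approximation: SE = √[(0.38×0.62 + 0.25)/46] = 0.1027; 1 - Φ(1.96 - 0.03/0.1027) = 1 - Φ(1.67) = 4.8%, close to the exact 4.6%.

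If patients changed in both directions at the same share, the figures would be 4.6% at 10% and 8.2% at 20%.

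**3. How far dilution alone can go.** If the arms became identical at 50% healing, the expected difference would be zero. An observed difference of zero has a lower limit of -1.96 × √(0.5/46) = -20.4 points, which fails. With 23/46 healed on Coban2, Andoflex needs at least 26/46 (+6.5 points) to pass. The chance of that outcome or its equivalents is about 30%.

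**4. Per-protocol alone.** Extreme case: 20% of the Andoflex arm change, all are non-healers, and all are dropped. About 37 remain (46 × 0.8 = 36.8), healing at 0.35/0.80 = 43.75%. Against 50% on Coban2 the expected difference is -6.25 points, and the per-protocol analysis passes 12.7% of the time.

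**5. Requiring both.** Simulated with one-way changes unrelated to prognosis and changers left out of the per-protocol set, the false-claim rate is 2.1-2.2% for 10% to 40% changing. With changes confined to non-healers, at 20% changing, accepting either set gives 12.5-17% false claims and requiring both gives 4.6-11%. Requiring both does not restore 2.5% in that setting, but it is always the better rule.

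**6. Power cost.** At the planned 65% v 50%, with changes unrelated to prognosis, power goes from about 79% (intention-to-treat alone) to about 77% (both) at 10% changing, and from about 74% to about 72% at 20%.

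**The case against.** **Patients are not shown to move to the comparator.** The text speaks only of an alternative bandage, and Appendix 3 offers other products. Changes need a clinical indication or intolerance, and entry is limited to patients who tolerate compression and have no known intolerance or allergy to the materials. This stands: Coban2 Lite is a plausible replacement, inferred from its usual-care status, and no share can be predicted.

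**Silence is not permission.** A reader might infer that a pass on intention-to-treat alone is enough. No sentence says so. That patients who change still count in their allocated arm also follows only from the intention-to-treat principle and is not stated. What remains is that the criterion is open.

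**This may be left to the SAP.** Membership of the per-protocol set often is, and a SAP may exist. But 8.2 has already fixed the success criterion, and which analysis must meet it is part of that criterion.

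**The figures are an upper bound and point one way.** Late, brief or reversed changes dilute less. If Andoflex is better, as planned, one-way changing lowers the chance of passing: 83%, 74% and 64% at 0%, 20% and 40%. Both points are right. The error rate, however, is judged where Andoflex is worse by the margin.

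**Excluding changers selects on outcome.** Also right, as step 4 shows. In particular, a rule that drops patients who changed before their ulcer healed can never drop an early healer. The per-protocol rule has to avoid this.

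**Conclusion.** The point holds in a limited form. Section 8.2 applies one -15 point limit to two analyses without saying which decides, while Appendix 2 permits changes that can bias either of them towards the claim. Under the stated assumptions (46 per arm, 50% v 35%, one-way changes, full Coban2 healing rate in changers), the intention-to-treat error rises from 2.4% to 3.3%, 4.6% and 8.2% at 10%, 20% and 40% changing.

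A reader might infer that crossover alone could produce a non-inferiority claim. The figures do not support that. Even with the arms made identical at 50% healing, the trial fails about 70% of the time, and chance must supply about 6.5 points in Andoflex's favour. Crossover raises the risk of a false claim; it does not make the claim by itself. Nothing here bears on whether bandage changes should be clinically allowed.

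**What to change.** In section 8.2 only:

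1. State that non-inferiority is claimed only if the lower 95% limit is not below -15 points in both the intention-to-treat and the per-protocol analyses.
2. Class patients who change bandage by a rule fixed before the data are analysed that does not depend on healing status.
3. Report bandage changes by arm, product and reason.

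Leave the care rule in Appendix 2 unchanged.

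The cost is the small loss of power shown above, about 1 to 2 points at 10% to 20% changing. It is also slightly more than wording: Appendix 2 asks for date and reason but not explicitly for the replacement product, so the product must be recorded too. Bandage use and healing are scheduled for assessment only at weeks 0, 6 and 12 (Table 3), so a rule that needs to know whether a change came before or after healing would often be unworkable as well as biased.

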Patient population	
 
Pragmatic approach to allow inclusion of wider cohort of patients than those with pure venous leg ulcers (VLU).
 
Therefore, patients with leg ulcer who are suitable for reduced (ie 'Lite') compression are considered for inclusion.
 
Specifically, these are: 
 
VLU
 
Mixed venous and arterial leg ulcers
 
 
 
Suitability for reduced compression is an ABPI of 0.5 -0.8 depending on holistic assessment. ABPI measured within last 3 months is part of the decision making to use reduced (Lite) rather than full compression. Only if ABPI or other diagnostic method (eg pulse palpation and ultrasound diagnostics, toe pressure assessment or arterial imaging) is not available or applicable then provision of solely a clinical assessment is allowed.
 

Sample size	
 
A total of 92 participants, over the age of eighteen, with leg ulcers. Power beta of 80%, one-sided alpha p-value of 0.025, non-inferiority limit 15%. Assumption of 15% difference in absolute percentage healed ulcers in intervention (Andoflex) arm versus control (Coban2) arm.
 
Therefore, 97.5% confidence interval for Andoflex to be no more than 15% worse than mean ulcers healed percentage for Coban2.
 
Sample size with 10% attrition rate included: 92 patients Of which: 
 
46 Patients to receive Andoflex TLC Calamine Lite
 
46 Patients to receive Coban2 Lite
 
 
 
Participants must have the capacity to provide informed written consent and complete patient reported outcome measures. Participants are recruited from the local community nursing caseload and identified in hospital clinics.
 

	Randomisation will be stratified for ulcer size, with cut-off	
	PUSH score of up to and including 10, or 11 and above.	
Sponsor	North Cumbria Integrated Care NHS Foundation Trust	
5001301	North Cumbra integrated care with roundation must	
Manufacturer & funder	Milliken Healthcare Inc	
	UK-based contact: [name], Clinical Specialist EMEA ,	
	Milliken Healthcare Division, [name] ,	
	[contact]	
Chief Investigator	[name], vascular specialist nurse, Vascular Surgery	
	Dept, North Cumbria University Hospitals NHS Trust.	
	[contact]	
Co-investigators	[name] PhD, Research Project Lead, [contact];	
	Cumbria Partnership NHS Foundation Trust	
	R&D Department, Carleton Clinic	
	[name]	
	[contact]	
	[name], GPwSI Research, Cumbria Partnership NHS	

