#### 5.4 Follow-up and Standard care

Patients are in the study for the planned 12 weeks, even if the index leg ulcer has healed prior to that time point. Apart from the specific research measurements and assessments, the patient will be followed up as they would in normal clinical practice. The vascular or community nurse will redress the leg ulcer as per routine care, and will conduct the measurement of the leg ulcer (grid measurement and PUSH score). The researcher will visit the patient at baseline, week 6 and 12 of study participation to randomise the patient and conduct the questionnaires.

Patients identified in the community (primary care or non-vascular surgery dept) can be invited to participate in the study via the vascular surgery department.

Standard wound care will be provided throughout the trial period, as well as meeting any other medical needs that arise. The SIGN guidelines for leg ulcer care form the framework for management of the leg ulcers (https://www.sign.ac.uk/media/1058/sign120.pdf).

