#### 6.3 Early withdrawal of subjects

Patients have the right to withdraw from the trial at any time and without giving any reason. If a patient withdraws from the trial, any and all information gathered prior to the withdrawal will be included in the analysis, though no further data collection will occur. If a patient does not attend planned follow-up appointments then two more attempts will be made to contact the patient regarding the study. If still no contact can be made then the patient is deemed lost to follow-up and any collected study data will be retained. Appendix 2, INTERVENTION DEVIATION AND LEG ULCER INFECTION, covers study withdrawals in more detail.

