#### Infection and use of antibiotics during trial

Patients do not have to withdraw from the study if infection occurs, as long as clinically there is a reason to continue with compression bandaging and it is deemed safe to do so. This applies for both oral and intravenous antibiotics use. If a treating clinician determines that compression bandaging should stop then this will be classed as an intervention deviation – see above.

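### Appendix 2 leaves two discretionary exits from the study that need no withdrawn consent, after which week-12 wound status is not observed and safety follow-up stops

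*Protocol*

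**What the plan says.** Appendix 2 of the protocol lists what may be decided when a patient stops or pauses the allocated bandage. Most options keep the patient in. On stopping compression it says: "Even if leg ulcer persists and patient no longer wears compression bandage, they can still continue in the trial if they wish", with outcomes still recorded on the planned dates. A change of bandage is allowed, and a pause for an adverse event does not in itself end participation.

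Two routes do lead out without the patient asking:

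- **After an adverse-event pause.** "Patient can remain in trial provided they are capable to continue with follow-up schedule and completion of outcome measures". If that is not possible, the reader is sent to the withdrawal option.
- **On clinical grounds.** This stands beside withdrawal at the patient's request. The example is deterioration that needs emergency treatment and puts a return to compression out of reach within a reasonable time.

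In the infection paragraph of the same appendix, patients need not withdraw "as long as clinically there is a reason to continue with compression bandaging" and this is judged safe. If the clinician stops compression, that is an intervention deviation, handled by the options above.

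After withdrawal, section 6.3 keeps the data already gathered, "though no further data collection will occur". Appendix 2 still asks for VEINES-QoL at the next time point, but for neither wound status nor adverse events. In the non-inferiority analysis of section 8.2, patients who withdraw or miss week 12 "will be assigned the worst-case healing outcome (not healed at week 12"). The same section also applies multiple imputation to missing outcome values.

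The primary outcome (5.5.1) is closure of the index ulcer. By section 5.4 the vascular or community nurse who redresses the ulcer in routine care "will conduct the measurement of the leg ulcer".

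**The concern.** Stopping a bandage and leaving a study are different events. A patient who can no longer wear compression, or is too unwell for the questionnaires, can usually still have the index site looked at, because a nurse is already dressing it. Under these two routes the patient may nevertheless leave the study, and the healing result then comes from a scoring rule instead of an observation.

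Three features make this matter here. First, a reaction to the bandage is among the appendix's own triggers, so exits can plausibly differ between arms. Second, participants cannot be blinded, section 6.1.1 claims blinding only for the statistical analysis, and the staff who decide on withdrawal are not stated to be blinded. Third, in a non-inferiority comparison, counting extra control patients as not healed moves the difference in favour of the new bandage. The same exits end safety follow-up in patients who have just had an adverse event or a deterioration.

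**Working it through.** **Inputs.** Healing 65% (Andoflex) and 50% (Coban2), margin 15 points, 1:1 allocation, 10% dropout, 92 patients (46 per arm): section 6.1 and Table 4. Error level: "one-sided alpha p-value of 0.025" (protocol summary). Section 6.1 says that the calculations "assume 80% power and 2.5% one-sided confidence interval".

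**Reproducing the planned size.** n per arm = [pC(1−pC) + pA(1−pA)] × (1.960 + 0.842)² / (pA − pC + 0.15)²
= (0.2500 + 0.2275) × 7.849 / 0.30² = 41.64, so 42 per arm and 84 in total. 84 × 1.10 = 92.4, in line with the stated 92. Dividing by 0.90 instead gives 47 per arm, 94 in total. The size is not in dispute.

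**Baseline.** Withdrawn patients stay in the denominator as not healed, so I use all 46 per arm.
SE = √{[pA(1−pA) + pC(1−pC)] / 46}, and P(declare non-inferiority) = Φ[(pA − pC + 0.15)/SE − 1.960].

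- On the margin (35% v 50%): SE = 0.1019, Φ(0 − 1.960) = 2.5%.
- At the planned rates (65% v 50%): SE = 0.1019, Φ(0.30/0.1019 − 1.960) = Φ(0.985) = 83.8%.

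**Effect of exits.** If k extra patients in one arm are withdrawn, and each would have healed with probability h, the scored healing rate in that arm falls by k × h / 46. The protocol gives neither k nor h, so both are assumptions.

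Worked case, k = 3, h = full arm rate:

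- Extra Coban2 exits on the margin: pC = 0.50 − 3 × 0.50/46 = 0.4674. (0.35 − 0.4674 + 0.15)/0.1018 = 0.320, and Φ(−1.640) = 5.1%.
- Extra Andoflex exits at the planned rates: pA = 0.65 − 3 × 0.65/46 = 0.6076. (0.6076 − 0.50 + 0.15)/0.1030 = 2.50, and Φ(0.54) = 70.5%.

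Worked case, k = 3, h = 10%:

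- pC = 0.50 − 0.30/46 = 0.4935. 0.0065/0.1019 = 0.064, and Φ(−1.896) = 2.9%.
- pA = 0.65 − 0.30/46 = 0.6435. 0.2935/0.1021 = 2.875, and Φ(0.915) = 82.0%.

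| Extra exits, one arm only | Would-be healing rate h | Error at margin (exits in Coban2) | Power (exits in Andoflex) |
|---|---|---|---|
| 0 | – | 2.5% | 83.8% |
| 1 | 10% | 2.6% | 83.2% |
| 1 | full arm rate | 3.2% | 79.8% |
| 2 | full arm rate | 4.0% | 75.4% |
| 3 | 0% | 2.5% | 83.8% |
| 3 | 10% | 2.9% | 82.0% |
| 3 | 20% | 3.3% | 80.1% |
| 3 | half the arm rate | 3.6% | 77.6% |
| 3 | full arm rate | 5.1% | 70.5% |

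With three exits in each arm at full arm rates, error is 3.1% and power 80.5%.

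**The case against.** The strongest reply is that Appendix 2 already does most of what is wanted, and that a reader could easily take too much from it. Five such readings are not supported.

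- **That staying in compression or completing questionnaires is a general condition of participation.** It is not. Patients off compression may continue, and the adverse-event condition covers the visit schedule and all outcome measures, among which Table 3 lists wound status, ulcer size and PUSH.
- **That patients with an adverse event or deterioration are withdrawn as a rule.** The options are worded as decisions that can be made, and deterioration is given as an example.
- **That infection forces an exit.** The conditional wording can be read that way alone, but the next sentences class stopping compression as an intervention deviation, which leads back to options that include staying in.
- **That the patient drops out of the healing analysis and the event goes unreported.** Section 8.2 keeps the patient as not healed, and Appendix 2 requires a report when discontinuation is due to deterioration of the index wound or leg. What is missing is the observed week-12 status and safety data after the exit.
- **That 5.1% error or 71% power is the expected damage.** Those figures need full arm healing rates and all three exits in one arm. Patients with emergency deterioration would probably heal less often.

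A further fair point is that a patient who cannot keep the schedule may miss week 12 anyway, and section 8.2 scores non-attenders the same way. The exit then costs little for the primary outcome unless wound status can be taken from nursing records. That limits the size, but the two exits remain, and so does the end of data collection that follows them.

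**Conclusion.** The point holds in a narrow form. Appendix 2 allows staff to end study participation in two situations without withdrawn consent. Sections 6.3 and 8.2 then replace an obtainable observation with a fixed result and end safety follow-up. Sections 6.3 and Appendix 2 also disagree on whether anything is collected after withdrawal.

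The statistical effect is probably small to moderate and cannot be fixed from the protocol. For three extra exits in one arm it runs from nil (none would have healed), through 2.9% error or 82% power (10% would have), to 5.1% or 71% as the upper end. This assumes 46 per arm, the planned rates, a normal approximation and the worst-case scoring of section 8.2. The loss of later safety data does not depend on these assumptions. This is a cheap improvement to the plan; it does not invalidate the design.

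**What to change.** In Appendix 2 and section 6.3, separate stopping or pausing the bandage from leaving the study. State that a patient who stops for an adverse event or deterioration, or who cannot complete questionnaires, is still followed for week-12 wound status (by visit or from the routine nursing record) and for SAEs to week 12, unless the patient withdraws consent to this. Reconcile section 6.3, the options in Appendix 2 and its infection paragraph with that statement, including what is collected after an early finish. No decision about the bandage or about care needs to change.

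The cost is a wording amendment and one wound-status and SAE check for what should be a few patients already under nursing care. The downside is that some patients will have wound status but no questionnaires.
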